6.1.6 Follow-up outcomes

6.1.6.1 Proportion of children attending scheduled follow-up at the same facility by Day 7

Attendance of scheduled follow-up at the same facility will be evaluated from:

ξ Scheduled and unscheduled visits form

A child will be counted in the numerator if:

- a follow-up visit advice is recorded at Day 0 and
- a follow-up visit for the child is found in the scheduled/unscheduled visits form and
- the follow-up visit is within 7 days of Day 0 (7th day included) and conducted at the enrollment facility

All children recruited will be in the denominator.

Additionally, the proportion will be calculated and reported using only children for whom a follow-up visit advice is recorded at Day0 as denominator.

Children for whom a scheduled follow-up visit is not found in the scheduled/unscheduled visit form will be assumed to not have attended scheduled follow-up at the same facility by Day 7.

ξ Day 7 follow-up form

A child will be counted in the numerator if:

- a follow-up visit advice is recorded at Day 0 and
- the caregiver reports visiting a government / public facility (non hospital) between child's enrollment and Day 7 follow-up visit date and
- Day 7 follow-up date is within 7 days of Day 0, considering a + 3 days window (10th day included).

All children recruited will be in the denominator.

Additionally, the proportion will be calculated and reported using only children for whom a follow-up visit advice is recorded at Day0 as denominator.

Children for whom no Day7 data are available or withdrew prematurely from the study will be assumed to not have attended scheduled follow-up at the same facility / government or public facility by Day 7.

6.1.6.2 Proportion of children presenting for unscheduled follow-up to any health facility by Day 7

Attendance of unscheduled follow-up at any health facility will be evaluated from:

ξ Scheduled and unscheduled visits form

A child will be counted in the numerator if:

- a follow-up visit advice is not recorded at Day 0 and
- a follow-up visit for the child is found in the scheduled/unscheduled visits form and
- the follow-up visit is within 7 days of Day 0 (7th day included)

All children recruited will be in the denominator.

Additionally, the proportion will be calculated and reported using only children for whom a follow-up visit advice is not recorded at Day0 as denominator.

ξ Day 7 follow-up form

A child will be counted in the numerator if:

- a follow-up visit advice is not recorded at Day 0 and
- the caregiver reports visiting a health facility (any, non-hospital) between child's enrollment and Day 7 follow-up visit date and
- Day 7 follow-up date is within 7 days of Day 0, considering a + 3 days window (10th day included).

All children recruited will be in the denominator.

Additionally, the proportion will be calculated and reported using only children for whom a follow-up visit advice is not recorded at Day0 as denominator.

Children for whom no Day7 data are available or withdrew prematurely from the study will be assumed to not have attended any health facility by Day 7.

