Additionally, visit information from government-designated hospital records will be collected retrospectively for children whose caregiver reported at Day 7 phone follow-up that they attended hospital, including clinical assessment on arrival (vital signs, admitting diagnosis), admission details (duration, if oxygen was administered, intensive care admission) and admission outcome (final diagnosis, discharge against medical advice, death). The same data will be collected for children who attended a non-hospital higher-level of care (emergency or admission unit of a primary or secondary care facility).

It is expected that some participants may present at the same or another health facility enrolled in the study during the follow-up period. These visits and the findings will be recorded on the appropriate scheduled / unscheduled visit eCRFs.

[figure not shown]
[figure not shown]
[figure not shown]

Fig. 5. Flowchart of the pre-post study. CDSA = Clinical Decision Support Algorithm. CG = Caregiver. HCP = Healthcare provider. OPD = Out-patient department.

Tab. 4. Schedule of the visits and associated CRFs for the pre-post study. The different types of staff collecting data are represented by the following icons:

Research assistant rotating
between different referral health
facilities

Call centre-based research assistant

		Health facility baseline visit		Higher level of care visit ^{1,2}		Follow-up or unscheduled visit at enrolled health facility		Phone follow-up
		Time point		Day 0		Day 0-7		Day 7 [7 - 10]
		Data collection method		Prospective data collection		Review of medical records		Phone interviews
		Study phase		Pre	Post ³			Pre
Events		Forms						Post ³
Informed consent				-				
Screening				TIMCI-01				
Identification & contact information	Full identification	TIMCI-02a						
	Contact information	TIMCI-02b						
	Identification and contact information check	TIMCI-02c						
	Referral facility identification	TIMCI-02d						
	Follow-up identification check	TIMCI-02e						
Socio-demographics		TIMCI-03						
Visit info	Care seeking behaviour, transport and costs for visiting health facility reported by caregiver	TIMCI-04a						
	Visit and admission info recorded by referral facility (medical records, registries) ²	TIMCI-04b						
	Patient journey reported by caregiver at follow-up	TIMCI-04c						
Clinical presentation & medical history	Clinical presentation and medical history reported by caregiver at baseline	TIMCI-05a						

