3.1.4 Outcomes

This section provides an overview of the outcomes as listed in the protocol.

Primary outcomes

- ξ Proportion of children referred by a primary healthcare provider to a higher level of care at Day 0 consultation
- ξ Proportion of children prescribed an antibiotic at Day 0

Secondary outcomes

- ξ Proportion of children with a severe complication by Day 7
- ξ Proportion of children admitted to hospital within 24 hours of the Day 0 consultation and as a result of a referral (this is a proxy for 'appropriate referral' of children)
- ξ Proportion of children cured at Day 7 follow-up
- ξ Proportion of children who completed referral as reported at Day 7 follow-up

Other outcomes of interest – hypoxaemia (in post-intervention only)

- ξ Proportion of children with severe ($\text{SpO}_2 < 90\%$), moderate ($\text{SpO}_2 90 – 91\%$) and mild ($\text{SpO}_2 92 – 93\%$) hypoxaemia, adjusted for sites at high altitude
- ξ Proportion of children with hypoxaemia (according to differing cut-offs) with severe complication
- ξ Proportion of children with severe hypoxaemia not meeting any other clinical criteria for severe disease
- ξ Proportion of children referred with hypoxaemia who receive oxygen at hospital

Other outcomes of interest – referral and follow-up

- ξ Proportion of children with non-severe disease referred to a higher level of care on Day 0
- ξ Average length of stay (in days) of children admitted to hospital
- ξ Proportion of children attending scheduled follow-up at the same facility by Day 7
- ξ Proportion of children presenting for unscheduled follow-up to any health facility by Day 7

Other outcomes of interest – antimicrobial prescription

- ξ Proportion of children prescribed a diagnosis-appropriate antibiotic
- ξ Proportion of febrile children tested for malaria at Day 0
- ξ Proportion of malaria positive children prescribed an antimalarial
- ξ Proportion of malaria negative children prescribed an antimalarial
- ξ Proportion of untested children prescribed an antimalarial

Other factors for exploratory analyses

- ξ Additional socio-demographic characteristics, urban / rural location, distance from health facility, key household indicators such as maternal age and education
- ξ Main complaint / symptom categories (including cough / difficulty breathing, fever, diarrhoea and other) and time since onset of symptoms
- ξ Alternative hypoxaemia cut-offs
- ξ Health care provider severity classification

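### Scheduled and unscheduled return visits are told apart by whether follow-up advice was recorded at Day 0, not by the visit itself, so early unplanned returns count as scheduled and a change in advice shifts both outcomes

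*SAP*

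**What the plan says.** SAP 6.1.6 defines each follow-up outcome twice, once from the scheduled and unscheduled visits form and once from the Day 7 form.

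- **Scheduled, visits form (6.1.6.1).** Some advice to return was on record, a return was entered on the form, and timing and place are set as follows: "the follow-up visit is within 7 days of Day 0 (7th day included) and conducted at the enrollment facility".
- **Scheduled, Day 7 form (6.1.6.1).** Advice was recorded, "the caregiver reports visiting a government / public facility (non hospital) between child's enrollment and Day 7 follow-up visit date and" the call took place by day 10.
- **Unscheduled, visits form (6.1.6.2).** The form and 7-day window are the same, but with the condition that "a follow-up visit advice is not recorded at Day 0" and with no facility condition.
- **Unscheduled, Day 7 form (6.1.6.2).** No advice was recorded and "the caregiver reports visiting a health facility (any, non-hospital"), again with the call by day 10.

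The main denominator is every recruited child. As an addition, scheduled attendance is also reported among children with advice recorded, and unscheduled attendance among children without.

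SAP 3.1.4 names the second outcome as "Proportion of children presenting for unscheduled follow-up to any health facility by Day 7". Both outcomes belong to the other outcomes of interest. Under SAP 6.2.1 they are compared between periods with the same random-effects logistic model as the primary outcomes.

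Protocol 7.1.1 takes follow-up advice from clinical notes or registers, and research assistants ask the provider where the entry is unclear. Of return visits to study facilities, Protocol 6.5.1 says: "These visits and the findings will be recorded on the appropriate scheduled / unscheduled visit eCRFs".

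**The concern.** None of the four rules looks at the return visit's timing against the advice, at its reason, or at a visit type. The split rests on a Day 0 variable, with facility conditions added for the scheduled outcome.

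Two things follow. A worsening child who was given advice and comes back ahead of time is credited as good follow-up attendance, when the visit may be a sign of treatment failure. And the split depends on a provider behaviour that could differ between periods: the intervention adds a decision-support tool that issues recommendations on child management (Protocol 7.1.2). If more advice is given or written down afterwards, the all-recruited results show fewer unscheduled returns and better scheduled attendance, which reads as benefit, even if families return exactly as before. The covariates in SAP 6.2.2 and the sensitivity analyses in SAP 6.2.4 do not address advice recording or visit timing.

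**Working it through.** The documents give no rates for these outcomes, so there is no planned figure to reproduce. The rules can be checked by logic. The size can only be illustrated.

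**1. The rules side by side**

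| Source | Counts as scheduled | Counts as unscheduled |
|---|---|---|
| Visits form | advice recorded; any visit to Day 7; enrolment facility | advice not recorded; any visit to Day 7 |
| Day 7 form | advice recorded; any public non-hospital facility | advice not recorded; any non-hospital facility |

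- Advised child, back early and unplanned at the enrolment facility: scheduled on both sources if the caregiver also reports the visit.
- Advised child, unplanned visit to another study facility (visits form) or a private facility (Day 7 form): in neither numerator.
- Every advised child is a fixed zero for unscheduled follow-up but remains in its all-recruited denominator.

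**2. A shift in advice, with return unrelated to advice**

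Let r be the probability of any return to the enrolment facility by Day 7, and q the share with advice recorded. Then scheduled = r × q and unscheduled = r × (1 − q).

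Assume r = 10%, and q = 40% before and 60% after.

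- Scheduled: 0.10 × 0.40 = 4.0%, then 0.10 × 0.60 = 6.0%; odds ratio (0.06/0.94)/(0.04/0.96) = 1.53.
- Unscheduled: 0.10 × 0.60 = 6.0%, then 0.10 × 0.40 = 4.0%; odds ratio (0.04/0.96)/(0.06/0.94) = 0.65.
- Total returns: 10% in both periods.

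For r from 5% to 20% and shifts in q of 30 to 40%, 40 to 60% and 30 to 70%, the scheduled odds ratio runs from 1.34 to 2.55 and the unscheduled one from 0.85 to 0.39. These are crude odds ratios, without covariates or clustering. In this model both additional-denominator proportions stay at r, so they show no change.

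**3. A shift in recording only, with return dependent on advice**

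Assume advice is given to 60% in both periods, recorded for 50% of those before and 90% after, with return in 20% of advised and 5% of unadvised children.

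- Recorded share: 0.6 × 0.5 = 30%, then 0.6 × 0.9 = 54%.
- Scheduled: 0.30 × 0.20 = 6.0%, then 0.54 × 0.20 = 10.8%.
- Unscheduled: 0.30 × 0.20 + 0.40 × 0.05 = 8.0%, then 0.06 × 0.20 + 0.40 × 0.05 = 3.2%.
- Total returns: 14.0% in both periods.
- Scheduled among those with recorded advice: 20% in both periods.
- Unscheduled among those without: 0.080/0.70 = 11.4%, then 0.032/0.46 = 7.0% (odds ratio 0.58).

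Here the additional denominator holds for the scheduled outcome but not for the unscheduled one.

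**4. Early returns inside the scheduled numerator**

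If 10% of advised children attend as planned and 2% to 5% come back early because they are worse, the unplanned share of the scheduled numerator is 2/12 = 17% to 5/15 = 33%. No choice of denominator changes this.

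**5. The hospital gap**

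Take an unreferred child whose caregiver reports at Day 7 a hospital visit without admission. The unscheduled Day 7 rule excludes hospitals. Completed referral (SAP 6.1.2.5) and 24-hour admission (6.1.2.2) both require referral advice. Severe complication (6.1.2.1) requires death or hospitalisation. If hospitalisation in SAP 6.1.1 is read as needing an overnight stay, that visit enters no re-attendance or hospital outcome.

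**The case against.** - **The plan already reports conditional proportions.** This stands in part. If return is unrelated to advice, they stay constant and would sit beside the moving all-recruited figures. The ratio of the two scheduled proportions even gives the share advised. But step 3 shows that the unscheduled one can still move, and neither deals with early returns. A reader might infer that the extra denominators are no help at all; that is too strong.
- **Nothing shows that advice changes.** This is correct. No passage says that giving or recording advice will differ between periods, and clarification by research assistants reduces errors from unclear entries, though not necessarily from absent ones. A reader might infer that a large spurious fall in unscheduled visits is to be expected; the documents do not support a predicted size.
- **A real rise in advice is a legitimate effect.** For scheduled attendance over all recruited children this is arguable. It does not make a matching fall in unscheduled visits a fall in unplanned re-attendance.
- **The visit type is not known to exist.** A reader might infer from Protocol 6.5.1 that the type of each visit is collected and then ignored. The sentence on appropriate eCRFs suggests it, but Tab. 4 has a single column for follow-up or unscheduled visits and SAP 6.1.6 treats the form as one source. The CRF description is an appendix that is not among the documents, so a separate field is not established.
- **The stakes are low.** Both outcomes are in the lowest tier, and deterioration is also covered by severe complication, cure at Day 7 and the harms summary. This stands, and it limits the weight of the point.

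**Conclusion.** The definitions in SAP 6.1.6 measure return visits with and without recorded advice, not scheduled and unscheduled follow-up. That an advised child's early unplanned return can count as scheduled, and that no advised child can be unscheduled, follows from the text without any assumption.

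The shift between periods is conditional: it arises only if the frequency or recording of advice differs. A move of two percentage points in each outcome at a 10% return rate is an illustration, and every rate in the working is assumed. The mismatch between the any-facility label and the non-hospital rule is a separate and smaller fault. The point is worth correcting because the remedy is cheap, but it concerns two exploratory-level outcomes only.

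**What to change.** 1. Add to SAP 6.1.6 an outcome *any return visit to a health facility by Day 7, regardless of advice*, over all recruited children, and make it the main pre-post comparison for re-attendance. Advice recording cannot move it. State that hospital attendance after a Day 0 referral is left out, since completed referral already counts it.
2. Report the share of children with follow-up advice recorded, by period and country, beside the follow-up outcomes.
3. If the forms hold a visit type or an advised return day, use it to classify visits. If they do not, rename the existing outcomes *return visit with recorded follow-up advice* and *return visit without recorded follow-up advice*.
4. In the Day 7 rule for unscheduled follow-up, either include hospital visits made without a referral or rename the outcome *non-hospital facility*.

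The cost is SAP wording and one extra row per table. Items 1, 2 and 4 use data that the SAP already plans to analyse. If a visit-type field is used under item 3, some visits may be misrecorded.

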6.2 Analysis Methods

6.2.1 Analytical Methods

For the primary analysis, pre-intervention and post-intervention periods will be defined as follow:

Pre-intervention period: from the date of data collection start to the date healthcare providers left the facilities for training on the intervention

Post-intervention period: from the date healthcare providers returned to the facilities after training and the devices was delivered to the facilities to the end of data collection

As training was staggered for the facilities, the definitions above will be applied at the facility level.

Outcomes will be described for each time period using summary statistics. In particular, counts and percentages will be used for binary variables and reported with one decimal place; mean and standard deviation (SD) or median (IQR) for continuous variables depending on their

distribution. Mean and median will be displayed with one decimal place and SD and IQR will be presented with two decimal places.

The two primary outcomes will be assessed using a random effects logistic regression model with the cluster included as a random effect. If convergence issues arise due to sparse data, clusters may be dropped or combined to higher grouping level (e.g. district).

Results will be reported with odds ratios, risk differences and their associated 95% confidence intervals (CI).

Secondary outcomes and other binary outcomes of interest will be evaluated in the same way.

Other continuous outcomes of interest will be assessed using random effects linear regression model with the cluster included as a random effect. Results will be reported in terms of adjusted mean differences with associated 95% CIs.

Modelling of secondary outcomes will be performed if numbers allow.

Further exploratory analysis, including interrupted time series analysis to assess change over time and data linked between the quasi-experimental pre-post study and the SPA and time-flow studies. These fall outside the scope of this SAP and will be detailed in a separate document.

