pneumonia management and offering outpatient treatment of possible serious bacterial infection in young infants when referral is not feasible. Per WHO curricula, the trainings for these updates include clinical sessions with visits to health facilities to see real life patients, which is out of the scope of the TIMCI project. To expedite the updated IMCI training process, PATH may provide financial support to ensure that these trainings are conducted in TIMCI areas if necessary. PATH in partnership with the MOH in each country will agree on which day of the IMCI training the pulse oximetry and CDSA modules will be included. Trainings will be conducted using a "train the trainers" approach, leveraging the experience of MOH IMCI trainers. Moreover, supervisors will also be included in training sessions to equip them for their supportive supervision role.

The pulse oximetry training session will be interactive, in line with adult learning principles, and with sessions that allow hands-on practice using the device. At the end of the training session, a post-training written test and one observation of the use of the pulse oximetry per participant will be used to determine immediate acquisition of knowledge and skill. If incorrect answers or limited skills were observed, the trainer will reinforce the correct concepts and provide supportive guidance and encouragement to correct use of the device. At the end of the CDSA training session, a post-training practical test based on a set of pre-recorded cases will be used to determine immediate acquisition of knowledge and skills. Competency evaluation will be extended post-course by asking trainees to perform a certain number of consultations while using the CDSA and including a minimum number of classical IMCI conditions.

In the case of staff turnover in TIMCI facilities detected during monitoring visits, PATH in consultation with the MOH will elaborate a plan for training such new staff either at the facility or in a group session elsewhere, depending on circumstances at the time.

Supervision

As per training, PATH will work with each MOH to integrate pulse oximetry and CDSA use into existing supervision mechanisms where possible. Supportive supervision for CDSA may additionally include personalized feedback directly informed by data recorded in the device. Intensive mentoring / supervision will be conducted following training, and then will be gradually tapered and fully transferred to government mechanisms.

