6.6.1 Quasi-experimental pre-post study

The sample size for the quasi-experimental pre-post study is calculated separately for each country, based on comparison between pre- and post-intervention periods.. The following assumptions are used:

- ξ power 80%
- ξ alpha 0.05
- ξ pre-intervention referral to a higher level of care 3% (based on informal estimates from country research teams and SPA data from various countries), with a minimum detectable difference of 50%
 - We have chosen a large detectable difference for referral from primary care as not all children referred will complete referral, i.e. a 50% increase in referral rate may only result in a 20 – 30% total increase in completed referrals (this will be assessed as a secondary outcome and is therefore not a component of the sample size calculation)
- ξ pre-intervention antibiotic prescription of 60% (based on informal estimates from countries, SPA data and other observational studies)
- ξ intra-cluster correlation coefficient (ICC) of 0.005 for referral and 0.05 for antimicrobial prescription

- ξ Kenya – estimated average cluster size of 230 children / month (assuming a cluster ratio of health centres : dispensaries 1:2, with 100 / month in dispensaries and 500 / month in health centres)
- ξ Senegal – estimated cluster size of 170 children per month (based on DHIS2 data on outpatient consultations in Thies in 2019)

For the referral primary outcome, we therefore initially estimated requiring the following sample size:

- ξ Kenya – 17 facilities, recruiting an average of 690 children per facility in each period, equating to 11,730 children per period
- ξ Senegal – 18 facilities, recruiting an average of 510 children per facility in each period, equating to 9,180 children per period

For the antibiotic prescription primary outcome, this would enable a minimum detectable reduction of 18% in Kenya and Senegal.

Following lower than anticipated recruitment in the pre-intervention period, sample size calculation was revised. As a result, two additional facilities were added per country and the pre-intervention period was extended from an initially anticipated 3 months to a 6 – 8 month period. A decision was also taken to target a post-intervention sample size of at least the same as the pre-intervention sample size, as well as a minimum duration of 9 months post-intervention to allow for stabilisation over time and some seasonal overlap of pre- and post-intervention periods.

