IDIs with caregivers: A purposive sample of caregivers will be selected for IDIs including those who completed referral (and arrived in the hospital within 24 hours) as well as those that did not adhere to the advice, and those that were not referred. Within these sub-categories, participants will be purposively selected with varying socio-demographic characteristics such as rural / urban location, age of caregiver/child, and education. An estimated total of 35-45 IDIs with caregivers in each country throughout the entire project are expected. Approximately 10 – 12 in-depth interviews with caregivers will be conducted across different time points (pilot, early, mid and late intervention) within one geographical area of each country. However, if geographical variation in health-seeking behaviour and outcomes is felt to be significant, fewer time points may be selected in favour of greater geographical diversity. In Kenya and Senegal only, a further 10-12 IDIs will also take place in the pre-intervention phase. Caregivers for IDIs will be different from FGD participants.

FGDs with caregivers: One geographical area will be selected per country, in which a total of 6 FGDs (3 in urban and 3 in rural location) will be conducted, each with 8 – 12 participants. These will be divided between early and late intervention. Caregivers for FGDs will be different from IDI participants. Where possible participants will be divided by age groups and gender as well as number of children.

Walking interviews with caregivers: A purposive sample of 6 – 8 caregivers per country, having received referral advice for their sick child, will be selected towards the end of the intervention period. Care givers may be followed through (to IDI) if of interest; otherwise caregivers for walking interviews will be different for IDIs and FGDs.

IDIs with healthcare providers: An estimated total of 35– 45 IDIs during the intervention phase per country is expected, allowing to document change over time. This will include approximately 10 – 12 IDIs with healthcare providers at different time points (pilot, early, mid, late intervention), purposively selected from facilities with divergent implementation. In Kenya and Senegal only, a further 10-12 IDIs will also take place in the pre-intervention phase. Where possible, some healthcare providers will be interviewed repeatedly over time.

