7.3.1 Quasi-experimental pre-post study

Analysis will include all eligible, consenting and enrolled children. Baseline characteristics will be described by country and across all study time points with summary statistics such as median and interquartile range or number and percentage. Outcomes will be described for each time period using summary statistics and results from the pre-intervention period and the post-intervention period will be compared. The two primary outcomes will be assessed using a random effects logistic regression models with the cluster (facility) included as a random effect. All models will be adjusted for individual-level baseline characteristics such as gender and age whose distribution at the facility may have changed between the time periods. Results will be reported with odds ratios and 95% confidence intervals (CI). Binary secondary outcomes will be evaluated in the same way. Continuous secondary outcomes will be assessed using random effects linear regression models, reporting adjusted mean differences between time periods with 95% CIs.

We will conduct planned subgroup analysis of the primary outcomes to assess for potential effect modification in variables such as clinical presentation (particularly cough / difficulty breathing) and diagnosis (particularly severity classification). If these variables are found to be balanced between the two time periods, effect modification will be assessed by incorporating an interaction between the time period and the variable in the model, acknowledging that power will be low. Additional individual or facility level characteristics to be considered in the model will be further detailed in the statistical analysis plan (SAP).

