2.2 Objectives

The overall goal of the TIMCI project is to reduce morbidity and mortality in sick children attending primary care facilities, while supporting the rational and efficient use of diagnostics and medicines by health care providers (HCP). The implementation research component of the project seeks to generate evidence on the health impact, operational priorities, cost and cost-effectiveness of introducing pulse oximetry embedded into a CDSA, into primary care in

LMICs, for children 0 – 59 months of age, to facilitate national and international decision-making on scale-up.

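### The primary model's only random effect is a facility intercept, so if facilities change by different amounts its confidence intervals are too narrow: severely for antibiotic prescription, modestly to moderately for referral

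*SAP*

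**What the plan says.** SAP 6.2.1 gives the primary model: "The two primary outcomes will be assessed using a random effects logistic regression model with the cluster included as a random effect". Protocol 7.3.1 identifies the cluster as the facility: "random effects logistic regression models with the cluster (facility) included as a random effect". Secondary and other binary outcomes are handled in the same way.

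The rest of the SAP leaves the correlation structure unchanged:

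- **6.2.2** adjusts for patient-level covariates only.
- **6.2.3** moves to GEE only if a quadrature check fails. It mentions neither a robust variance nor a small-sample correction.
- **6.2.4** varies the encounters, the referral definition and the period dates.

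For sparse data, SAP 6.2.1 adds: "If convergence issues arise due to sparse data, clusters may be dropped or combined to higher grouping level (e.g. district").

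On timing, SAP 6.2.1 notes: "As training was staggered for the facilities, the definitions above will be applied at the facility level". Protocol 6.6.1 records that "two additional facilities were added per country and the pre-intervention period was extended", and expects only some seasonal overlap between the two periods.

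**The concern.** The pre/post contrast is made within facilities. A facility intercept absorbs stable differences between facilities, but the standard error of the period effect then contains only child-level variation. That is right only if all facilities move together, i.e. CAC = 1.

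The documents make this unlikely even with no intervention effect. Calendar windows differ by facility because training was staggered. Seasons overlap only in part. Facilities were added after baseline recruitment fell short, so their baseline windows presumably began later. Training section 6.3 also provides for staff changes ("In the case of staff turnover in TIMCI facilities detected during monitoring visits"). If the intervention works, uneven uptake adds to this: Protocol 6.6.2 plans interviews with providers "purposively selected from facilities with divergent implementation".

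The evidence is meant "to facilitate national and international decision-making on scale-up" (SAP 2.2), so variation in change between facilities belongs in the interval. Leaving it out pushes towards false positives. The quadrature check tests numerical integration and would not detect the problem.

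**Working it through.** **Inputs (Protocol 6.6.1, SAP 3.4).** Two-sided alpha 0.05; power 80%; referral 3% vs 4.5%, ICC 0.005; antibiotics 60%, ICC 0.05; Kenya 17 facilities with m = 690 per period; Senegal 18 with m = 510. CAC is not in the documents and is varied here.

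**1. Reproduce the plan.** Individual n per period = (1.96 + 0.8416)² × (0.03×0.97 + 0.045×0.955) / 0.015², which rounds up to 2,515. The design effect is 1 + (m−1)×ICC.

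- Kenya: 1 + 689×0.005 = 4.445; 2,515 × 4.445 ≈ 11,179; /690 = 16.2, so 17 facilities.
- Senegal: 1 + 509×0.005 = 3.545; 2,515 × 3.545 ≈ 8,916; /510 = 17.5, so 18 facilities.

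Both match. The sizing therefore treated pre and post as independent facility samples (in effect CAC = 0), whereas the analysis assumes CAC = 1.

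**2. SE understatement.** Let σ² = p(1−p), with k facilities.

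- Variance under the planned model: 2σ²(1−ICC)/(km)
- True variance: 2σ²[(1−ICC)/(km) + ICC(1−CAC)/k]
- SE ratio R = √[1 + m×ICC×(1−CAC)/(1−ICC)]
- Coverage = 2Φ(1.96/R) − 1; type I error = 1 − coverage

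Example, Kenya antibiotics at CAC 0.9: R = √(1 + 690×0.05×0.1/0.95) = √4.63 = 2.15.

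| Outcome | CAC | R, Senegal / Kenya | Coverage, Senegal / Kenya | Type I error |
|---|---|---|---|---|
| Antibiotics | 0.95 | 1.53 / 1.68 | 80.0% / 75.7% | 20–24% |
| Antibiotics | 0.9 | 1.92 / 2.15 | 69.3% / 63.8% | 31–36% |
| Antibiotics | 0.8 | 2.52 / 2.87 | 56.3% / 50.5% | 44–50% |
| Referral | 0.9 | 1.12 / 1.16 | 92.0% / 90.9% | 8–9% |
| Referral | 0.8 | 1.23 / 1.30 | 88.9% / 86.8% | 11–13% |
| Referral | 0.5 | 1.51 / 1.65 | 80.6% / 76.4% | 19–24% |

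**3. What these CACs mean.** For antibiotics, the SD of facility-specific change is √[2×0.05×0.24×(1−CAC)]: about 4.9 percentage points at CAC 0.9 and 3.5 at CAC 0.95.

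**4. Unequal facility sizes.** Kenya's planning mix is 500 and 100 children per month in a 1:2 ratio, i.e. 1,500 and 300 per three-month period. The model weights by size, so the relevant m is Σm²/Σm = (1,500² + 2×300²)/(1,500 + 2×300) = 1,157. Type I error at CAC 0.9 and 0.8 is then 46% and 59% for antibiotics, 12% and 18% for referral.

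**5. Lower recruitment.** The achieved m is not stated. At an assumed m = 400, type I error at CAC 0.9 and 0.8 is 27% and 39% for antibiotics, 7% and 10% for referral. At an assumed m = 200, antibiotic coverage is 83% and 73%; referral coverage at CAC 0.8 is 93%.

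**6. Simulation.** Random-intercept logistic fits, 400 datasets per scenario, coverage at CAC 0.9 / 0.8:

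| | Kenya, equal sizes | Senegal, equal sizes | Kenya, 6×1,500 and 11×300 |
|---|---|---|---|
| Antibiotics | 62% / 52% | 72% / 62% | 55% / 42% |
| Referral | 90% / 84% | 94% / 88% | 88% / 79% |

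At CAC 1, coverage was 93–97%. A facility-level paired t interval covered 92–97% in every scenario. In separate null simulations (200 to 300 runs), a facility-by-period random effect with t on facilities−1 df rejected 1.7–8.5% of the time, and the paired t-test 3.0–6.5% (Monte Carlo SE about 1.3–1.6 points).

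**The case against.** The strongest reply is that every size above rests on a CAC and cluster sizes the documents do not supply; recruitment fell short and the revised size per facility is not given. With small clusters the referral error is negligible. The provision for staff turnover is a contingency, and the divergent-implementation wording concerns sampling for interviews. Uneven uptake is also effect heterogeneity, so it cannot support the null error rates. SAP 6.2.4 already plans calendar-matched and later-start analyses, and 6.2.2 adjusts for case mix. The facilities are not described as a random sample, so an interval for the average change in these facilities is arguable. A planned-size antibiotic effect would be found anyway, and a shift common to all facilities is the larger threat in an uncontrolled design.

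Much of this stands as qualification. The figures are conditional, those two passages are soft evidence, and the fix does nothing about a common shift. It does not rescue the planned interval. Staggered windows and partial seasonal overlap remain as sources of unequal change under the null. The 6.2.4 analyses change dates, not the variance, and use the same model. The antibiotic error is material even at CAC 0.95 with planned sizes, or at m = 200 with CAC 0.9. Given the scale-up aim, an interval confined to these facilities is not the one readers need.

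**Conclusion.** The concern holds. The planned interval is valid only if all facilities change by the same amount, and the plan's own sample size did not assume that. For antibiotic prescription the understatement is severe over plausible CACs: the SE is too small by a factor of about 1.5 to 2.9 for CAC 0.95 to 0.8. For referral it is modest at CAC 0.9 and moderate at 0.8, and becomes marked at 0.5 or with Kenya's unequal sizes. These statements rest on the planned ICCs, the stated cluster sizes and an assumed CAC; at CAC 1 the error is zero.

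Detection of the planned effect is not in doubt. For Kenya antibiotics at CAC 0.8 the correct SE is about 1.8 points, and the planned reduction (18% of 60% = 10.8 points) is about 6 of these. What is at stake is false claims from null or small changes, and overstated precision. Because this is the primary analysis, it should be corrected before the data are analysed.

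The sparse-data fallback is a smaller matter. Merging facilities into districts removes facility clustering, and dropping sparse clusters selects on the outcome. This affects mainly young infants and rare secondary outcomes.

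**What to change.** - **SAP 6.2.1:** add a facility-by-period random effect alongside the facility intercept in all pre/post models. Use a t reference based on the number of facilities (facilities minus 1 per country: 18 and 19 df with the revised 19 and 20 facilities), and report the estimated facility-by-period variance. A facility random slope for period is a distinct alternative that lets between-facility variance differ by period; the SAP should name one of the two.
- **SAP 6.2.3:** if GEE is used, cluster on facility with a small-sample-corrected robust variance.
- **Sparse data:** replace dropping or merging clusters with a facility-level paired pre/post analysis on risk differences, which the SAP already reports, so that zero-event facilities stay in. State the weighting and how the 6.2.2 covariates enter. The paired version simulated above used log odds ratios.

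**Cost.** SAP wording and a few lines of code; no new data. For Kenya antibiotics the planned-model SE is √(2×0.24×0.95/11,730) = 0.62 points, a half-width of 1.2 points. With the fix (17 facilities, 16 df, t = 2.12) it becomes 1.3 at CAC 1, 2.8 at CAC 0.9 and 3.8 at CAC 0.8. The sample size can bear this: at CAC 0.8 Kenya needs design effects, 1 + (m−1)×ICC − m×ICC×CAC, of about 1.7 for referral and 7.9 for antibiotics, against 4.4 and 35.5 in the plan's own calculation.
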